#### **Radiation dose:**

According to data published for fluorodeoxyglucose (FDG) PET the effective dose was 6.23 mSv [14]. Doses from FDG PET scanning to the gonads, uterus, and bladder were higher than to the other organs and were 5.0, 7.8, and 59.2 mSv, respectively. This is because of the final accumulation of  $^{18}\text{F}$  in the bladder. Other organ doses ranged from 2.5 to 4.8 mSv. The total effective doses of the combined PET/CT studies, calculated by summing the effective doses of CT and PET scanning ranged from 13.45 to 31.91 mSv for female patients and 13.65 to 32.18 mSv for male patients taking various CT protocols into consideration [14]. Average contrast-enhanced CT of abdomen and pelvis dose is 20 mSv [15].

In the phase I/II study  $^{68}\text{Ga}$ -OPS202, the calculated effective dose for an injection of 150 MBq (4 mCi) of  $^{68}\text{Ga}$ -OPS202 was 3.6 mSv, which is lower than the radioactivity dose of the FDA- and EMA-approved OctreoscanTM.

In this trial, each subject will get two PET/CT examinations with a 2- to 3-week interval between the two examinations. The total  $^{68}\text{Ga}$ -OPS202 in each 3-study arm will range from 140 to 340 MBq (calculated by summing the doses at Visit 2 and Visit 3). Based on phase I/II study, the total dose for the study will range from approximately 3.6 mSv to 7.5 mSv. The dose of two CTs will depend on the imaging protocols and will not exceed 20 mSv for each CT examination. Thus, total cumulative dose for two PET/CT examinations will range from approximately 44 to 48 mSv.

##### *6.1.1.1 Spillage*

All due precautions and site procedures should be implemented to prevent spillage or leakage of radiodiagnostics. Infusion bags, intravenous lines, venous access should all be secured and the connections thoroughly checked. The infusion line should be taped in a loop and taped to the subject to prevent direct tension between the line and the venous access.

Despite precautions, if spillage or leakage should occur, then the site procedures must be implemented to protect the subject, staff and members of the public from radiation exposure. The subject should be moved from the area of the spillage or leakage while the area is decontaminated. Details of the spillage or leakage should be recorded (including how the incident happened, the time of the incident, an estimate (if possible) of the amount of substance lost) and the measures taken. In addition, the incident is to be reported in the same manner as an adverse event using the MedDRA PT Product Leakage and as appropriate PT Occupational exposure to radiation (if there is exposure to staff) and PT Exposure to radiation (if there is exposure to the subject or members of the public).

##### **6.1.2 Other Investigational Medicinal Products**

There are no investigational products other than  $^{68}\text{Ga}$ -OPS202 in this study.

##### **6.1.3 Other Study Drugs**

Not applicable.

## 6.2 Concomitant Medication/Therapy

Any relevant prior or concomitant therapy or medication given to a subject within 3 months before IIP administration, during IIP administration and up to the end of the follow-up period will be indicated on the eCRF. Dose and generic name or tradename will be recorded.

The following concomitant medications /therapies are not permitted during this study up to the second PET/CT scan and 48 hours post second OPS202 scan:

- Administration of any radiopharmaceutical
- On Visit 2 and Visit 3 parenteral amino acid solutions and any formulation of diuretics are not allowed. Stable adjusted diuretics such as for subjects with hypertension are permitted.

Long acting SSAs, ie, Somatuline® Autogel® /Depot® (60, 90 or 120 mg) and Sandostatin® LAR (20 or 30 mg) will not be allowed within 28 days prior to the first Ga-OPS202 PET/CT exam (at Visit 2) and during the study up to Visit 3 after the second Ga-OPS202 PET/CT exam has been completed. Short acting Sandostatin® is allowed during the study with a washout period of 24 hours before each of the two Ga-OPS202 PET/CT (Visit 2 and Visit 3), to avoid possible interaction between the non-radioactive SSA and OPS202.

Subjects on long acting SSA who need to continue such treatment for symptom control, should be switched to short acting SSA with a 24 hour wash out period before each of the two Ga-OPS202 PET/CT (Visit 2 and Visit 3). Long acting SSAs can be resumed after Visit 3.

Other concomitant medications are permitted during this study at the discretion of the investigator but they must be monitored closely and every effort should be made to keep their dose and dose regimen constant throughout the course of the study.

## 6.3 Procedures for Monitoring Subject Compliance

The IIP is administered i.v. by the investigator or his/her delegate. Therefore, no specific procedure is required for monitoring subject compliance. The injected peptide mass dose and radioactivity dose will be recorded in the medical file and in the eCRF for each subject.

The investigator will ensure that the subject did not and is not taking any of the prohibited medication listed in Section 6.2 during the study period.

## 7 ASSESSMENT OF EFFICACY

For the timing of efficacy assessments in this study, refer to the schedule in [Table 5](#).

The sets of images obtained at Visit 2 and Visit 3 for the primary endpoint and most of the secondary endpoint analyses will be sent to an ICL for centralised blinded reading by two independent experienced radiologists/nuclear medicine physicians, and a third for adjudication of discordances. The readers will be specifically trained for this protocol. Full details of the read design and conduct will be provided in the IRC.

For the primary endpoint analysis, the number of lesions on each subject scan will be counted on a per organ basis by the two primary independent readers. Scans will be blinded to subject, site, peptide and radioactivity dose. In case of discrepancy, images will go to the adjudicator (third reader) for a final read and adjudication.

After blinded reading, the readers will compare the paired scan for each subject and note which of the pair provides superior images based on overall image quality and lesion count.

The primary endpoint is the mean number of lesions identified in each tabular cell (see [Table 3](#)) as the ratio of the maximum number of lesions identified per organ per subject, removing individually differing absolute lesion numbers as a confounder and allowing the factorial design to be established to identify the optimum peptide mass and radioactivity dose.

The sequence of image display and recording of results will be as follows on a per subject basis:

- 1) Review of the two image sets of  $^{68}\text{Ga}$ -OPS202 scans in randomised step-wise fashion, without and with CT image fusion. The PET and CT images acquired at the same time will be used for co-registration.
- 2) CT images for standard-of-truth assessments will be reviewed by two radiologists not involved in PET/CT images read. It is not anticipated that there will be a difference in the lesion counts between the two visits related to disease progression, due to slow development of GEP-NETs; however, there may be technical reasons for variations between the scans
- 3) Review of the lesion-to-background ratios in each major anatomical site (liver, lymph nodes, bone and lungs) based on the evaluation of up to five most avid lesions per organ
- 4)  $\text{SUV}_{\text{max}}$  calculations of the five most avid lesions per organ on PET scans (liver, lymph nodes, bone and lungs)
- 5) For image quality, direct comparison of the two  $^{68}\text{Ga}$ -OPS202 scans with different peptide and radioactivity doses
- 6) Evaluation of previously acquired ssrt2 receptor agonist positive scans.

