### **3.8 Maintenance of Randomisation and Blinding**

This is an open-label study; there is no blinding for the imaging product used nor for its doses (peptide mass dose as well as radioactivity dose). The scan images collected at Visit 2 and Visit 3 are to be read centrally in a blinded manner.

The images will be sent to a central imaging core lab ICL. The ICL will ensure that the Ga-OPS202 and CT images are initially presented to the readers in a blinded manner and randomised to temporal sequence. Blinding includes subject ID, site, type of scanner(s), peptide mass dose and radiation dose (and therefore visit number). Full details of this complex read will be provided in the Imaging Review Charter (IRC).

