### 7.1 Primary Efficacy Endpoint and Evaluation

For each combination of injected peptide/radioactivity dose ranges, differences in relative lesion counts derived from a  $2 \times 3$  factorial analysis measuring the ratio of the number of lesions detected by  $^{68}\text{Ga}$ -OPS202 to the number of lesions assessed by standard-of-truth: blinded read-out (derived from above recording of results, points 1 and 2) with descriptive analyses.

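### A subject's two OPS202 scans are counted in one per-subject reading step, and the text states nothing to keep the first count from guiding the second

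*Protocol*

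**What the plan says.** Protocol section 7, repeated in SAP 1.3.2.1, fixes the order of the central read: "The sequence of image display and recording of results will be as follows on a per subject basis". Six steps follow.

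- Step 1 reviews the subject's two OPS202 "scans in randomised step-wise fashion, without and with CT image fusion".
- Step 2 is the CT standard of truth, with its own readers: "CT images for standard-of-truth assessments will be reviewed by two radiologists not involved in PET/CT images read".
- Steps 3 and 4 are the lesion-to-background ratio and SUVmax.
- Step 5 compares the two OPS202 scans directly.
- Step 6 is the "Evaluation of previously acquired ssrt2 receptor agonist positive scans".

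Protocol 7.1 ties the primary endpoint to the first two steps: "blinded read-out (derived from above recording of results, points 1 and 2) with descriptive analyses". Step 1 therefore gives the numerator for both of a subject's scans, and step 2 gives the denominator.

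The stated protections are as follows. For the lesion count, "Scans will be blinded to subject, site, peptide and radioactivity dose". Protocol 3.8 adds masking of subject ID, scanner type and visit, and presentation in randomised temporal order. The preference read is placed later: "After blinded reading, the readers will compare the paired scan for each subject and note which of the pair provides superior images". Both documents leave the full read design to the imaging charter. The SAP also refers to a flow chart (Figure 2) that does not appear in the text available here.

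**The concern.** A reader shown a subject's pair knows that the anatomy is shared, even with the ID removed. A lesion seen on the clearer scan is then more likely to be looked for, and called, on the poorer one. This pulls the two counts of a pair towards each other. The per-subject display also fits poorly with the statement that the count is blinded to subject.

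The primary comparison is a difference in relative lesion counts between dose ranges. SAP 3.2.1.1 selects the optimal range by the highest observed relative lesion count, with 8 scans per combination and no tests or intervals. Shrinkage of true differences would feed straight into that choice. It would also run in the direction that Protocol 1.5 expects: little effect of peptide mass, and a clear signal across 100 to 200 MBq. It would flatter the 40-80 MBq range, for which the synopsis anticipates a poor signal.

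**Working it through.** **Plan figures.** The plan gives no figure for this effect and has no formal sample size. Its scan counts reproduce: 24 subjects × 2 = 48 scans; 48/6 = 8 per combination; 48/2 = 24 per peptide range; 48/3 = 16 per radioactivity range.

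**What each safeguard does about carry-over within a pair.**

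- Randomised order balances which scan is read first. It does not stop the first from guiding the second.
- Masking ID, site, scanner, dose and visit hides which dose is which. It does not hide that two scans shown together belong to one person.
- Separate CT readers protect the denominator, not the two PET counts.
- Placing the preference read after the blinded read protects the counts from that comparison, not from each other.

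The text states no separate session, interval, mixing across subjects or lock of the first count before the second scan is shown.

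**Expected size within a pair.** Read independently, let a be the lesions found on scan X only and b those found on scan Y only, so D = a − b. Assume a fraction r of partner-only lesions is added to whichever scan is read second, and that order is random 1:1.

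- X first: Y gains ra, so the difference is D − ra.
- Y first: X gains rb, so the difference is D + rb.
- Mean: D − r(a − b)/2 = D(1 − r/2).

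This does not require the lesions on one scan to be a subset of those on the other. SAP 3.2.1.1 uses one CT count per subject covering both visits, so dividing both counts by it leaves the factor unchanged.

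| r (assumed) | 1 − r/2 | Loss | D = 0.20 (illustrative) becomes |
|---|---|---|---|
| 0 | 1.000 | 0% | 0.200 |
| 0.25 | 0.875 | 12.5% | 0.175 |
| 0.5 | 0.750 | 25% | 0.150 |
| 1 | 0.500 | 50% | 0.100 |

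**Peptide contrast.** In all three sequences (Protocol Table 4) the lower peptide range is given at Visit 2 and the higher at Visit 3. The contrast is therefore the mean of within-pair differences and takes the full factor 1 − r/2.

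**Radioactivity contrast, 160-200 against 40-80 MBq.** This is only partly within pairs. The 40-80 range is paired with 100-140 in sequence A and with 160-200 in sequence C. The 160-200 range is paired with 100-140 in B and with 40-80 in C. Assume detection of 0.60, 0.75 and 0.80 in the three ranges; these are illustrative values, not document figures.

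- Nested detection: low = 0.60 + (r/2) × mean(0.15, 0.20) = 0.60 + 0.0875r; high = 0.80. Difference = 0.20 − 0.0875r.
- Independent detection: low = 0.60 + (r/2) × mean(0.75 × 0.40, 0.80 × 0.40) = 0.60 + 0.155r; high = 0.80 + (r/2) × mean(0.75 × 0.20, 0.60 × 0.20) = 0.80 + 0.0675r. The difference is again 0.20 − 0.0875r.

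The true 0.20 becomes 0.178 at r = 0.25, 0.156 at r = 0.5 and 0.1125 at r = 1. As a share of the true value these are 0.891, 0.781 and 0.5625.

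**Agonist scan.** It is step 6, while the primary endpoint uses steps 1 and 2. It feeds only exploratory comparison f) in SAP 3.2.1.2. Carry-over from OPS202 to the agonist read could only raise agonist sensitivity there, which would work against OPS202.

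**The case against.** The strongest objection is that the detail may exist elsewhere. Protocol 7.3 assigns the primary read design and the conduct of the read to the charter, and SAP Figure 2 shows the workflow. Either may already separate the two reads. The six steps also cannot be one reader's sitting. Step 2 belongs to other radiologists, and the SAP takes the lesions for steps 3 and 4 from those confirmed by CT, so it needs step 2 first. This stands: a reader might infer that every second count is made with the first in view, and the documents do not show that.

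A reader might also infer that the agonist scan takes part in shrinking the primary count. The step order and Protocol 7.1 rule that out. The CT denominator is likewise outside the chain.

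It can further be said that r has no source and may be zero, that D(1 − r/2) never reverses the expected sign within a pair, and that the analysis is descriptive. All of this stands, and no change in the selected dose range has been shown. Counting before the preference read is already the stated order; only an explicit lock is missing.

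Referral to the charter does not settle the matter, however. The protocol and SAP do more than stay silent: they specify a display order, and that order puts the pair together. None of the protections they state acts on carry-over between the two scans.

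**Conclusion.** The point holds as a risk in the stated reading order. Both primary counts of a subject come from one step of a per-subject display, with no stated separation or lock between them. If recall occurs, the direction is towards no difference, by a factor of 1 − r/2 for the peptide contrast and somewhat less for the radioactivity contrast illustrated above. The loss runs from nothing at r = 0 to half at r = 1. This rests on random 1:1 order, the same r in both directions, and carry-over that adds lesions but never removes them. The documents give no means of placing r within that range.

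They do not support a claim that the counts are in fact biased, that the blinding to dose fails, or that the dose selection would come out differently. The point merits a change because selection rests on observed counts from 8 scans per combination and the remedy is cheap.

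**What to change.** In Protocol 7, SAP 1.3.2.1 and the charter, replace the per-subject display for the OPS202 lesion count with these rules:

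- Give every OPS202 scan its own code, and pool and shuffle the scans across subjects.
- Read a subject's two scans in separate sessions with a stated minimum interval, its length set by the sponsor.
- Lock each count before the partner scan is shown, before the side-by-side preference read and before the agonist read.
- Apply the same rules to the adjudicating reader, whose read becomes final where the two readers differ.

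The per-subject display can stay for the CT standard of truth, which is defined over both visits together, and for the steps that follow the locked counts. If the charter already separates the reads, one sentence in each document stating the rule, in place of the current wording of step 1, is enough.

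The cost is wording in three documents and a longer read calendar. The readers and the number of reads stay the same.

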### 7.1 Primary Efficacy Endpoint and Evaluation

For each combination of injected peptide/radioactivity dose ranges, differences in relative lesion counts derived from a  $2 \times 3$  factorial analysis measuring the ratio of the number of lesions detected by  $^{68}\text{Ga}$ -OPS202 to the number of lesions assessed by standard-of-truth: blinded read-out (derived from above recording of results, points 1 and 2) with descriptive analyses.

### 7.2 Secondary Efficacy Endpoints and Evaluations

*Key Secondary Endpoint:*

- For each combination of injected peptide/radioactivity dose ranges, differences in image quality derived from a  $2 \times 3$  factorial analysis measuring the tumour-to-background ratio in each of the major anatomic sites (descriptive analyses for liver, lymph nodes, bone and lungs)

A qualitative analysis of the image quality as assessed by the blinded readers will be performed to back up the quantitative quality measured by tumour-to-background analysis.

For further details, refer to the IRC.

*Other Secondary Endpoints:*

- Differences of lesion  $SUV_{max}$  between the two peptide mass dose ranges and the three radioactivity dose ranges measured in the most avid lesions: descriptive analyses for up to a maximum of five lesions per organ (derived from above recording of results, point 4), in liver, lymph nodes, bone and lungs
- Differences of absolute number of lesions between the two peptide mass dose ranges and the three radioactivity dose ranges detected in each of the following anatomic sites, both as standalone and also compared to the standard-of-truth scans; blinded read-out (derived from above recording of results, points 1 and 2) with descriptive analyses:
  - Primary site of GEP-NET
  - Lymph nodes
  - Liver
  - Axial/appendicular skeleton
  - Lungs
- The primary and secondary endpoints will also be evaluated on a radioactivity dose/kg of body weight.

*Exploratory Endpoints:*

- Preliminary diagnostic sensitivity of  $^{68}\text{Ga}$ -OPS202 imaging of GEP-NETs by both subject-based and lesion-based analysis compared to standard-of-truth
- Comparison tosstr2 agonist positive scan results will be computed for sensitivity analysis
- Differences in  $SUV_{max}$  ratios between the two peptide mass dose ranges and three radioactivity dose ranges for lesions.
- SNR calculated from lesion-free VOI in the liver:  $SUV_{mean}/SUV_{SD}$  between the three radioactivity doses.

For further details on efficacy secondary endpoints assessment, refer to the IRC.

### **7.3 Methods and Timing of Assessing, Recording, and Analysing Efficacy Data**

Methods for assessing efficacy data are listed below and are described in further detail in the IRC. Timing of efficacy assessments are discussed in Section 5. Procedures for recording efficacy data are discussed in Section 14.1, and methods of analyses are discussed in Section 10.4.5.

All images will be sent to a central ICL for QC and central read management. This comprises the following images:

- Priorsstr2 agonist positive PET scans (see Section 4.1)
- All  $^{68}\text{Ga}$ -OPS202 PET/CT scans.

The details of imaging set management and read design will be fully described in the IRC. This will include the following:

- Full acquisition guidelines for the site
- Process for PET scanner quality control (phantom assessments and reporting)
- Image transmission methodology

- Core lab QC methodology and management of the images
- Read design for primary endpoint
- Read design for secondary endpoint and process for calculating tumour-to-background ratio and  $SUV_{max}$
- Design of exploratory endpoints
- Conduct of the read
- Management, training and inter-reader evaluation
- Data management
- Data export overview
- Archiving of images.

## 8 ASSESSMENT OF SAFETY

The safety and tolerability of  $^{68}\text{Ga}$ -OPS202 consists of evaluating:

- AEs throughout the study
- Clinical laboratory test results (serum chemistry, haematology, urinalysis) throughout the study
- Vital signs measurements (blood pressure and heart rate) throughout the study
- ECG at Visit 1 and 4 (End of treatment/ Early Withdrawal)
- Physical examination results throughout the study
- Concomitant medication usage throughout the study.

### 8.1 Adverse Events

Adverse events will be monitored from the time that the subject gives informed consent and throughout the study (see Section 3.5 for a definition of the study duration) and will be elicited by direct, nonleading questioning or by spontaneous reports. Further details for AE reporting can be found in Section 8.1.1.

#### Definition of an Adverse Event

An AE is the development of an undesirable medical condition or the deterioration of a pre-existing medical condition following or during exposure to a pharmaceutical product, whether or not considered causally related to the product. An undesirable medical condition can be symptoms (e.g. nausea, chest pain), signs (e.g. tachycardia, enlarged liver) or the abnormal results of an investigation (e.g. laboratory findings, electrocardiogram). In clinical studies, an AE can include an undesirable medical condition occurring at any time, including run in or washout periods, even if no IIP has been administered.

This definition includes events occurring from the time of the subject giving informed consent until the end of the study (as defined in Section 3.5).

#### 8.1.1 *Categorisation of Adverse Events*

##### 8.1.1.1 *Intensity Classification*

Adverse events will be recorded and graded according to the current version of the NCI-CTCAE (version 5.0). In view of meta-analyses, and for conversion purposes, the following conversion mapping will apply if the NCI-CTCAE scale is not available for a given AE:

- NCI-CTCAE Grade 1 corresponds to mild,
- NCI-CTCAE Grade 2 corresponds to moderate,
- NCI-CTCAE Grade 3 corresponds to severe,
- NCI-CTCAE Grade 4 corresponds to life threatening/disabling,
- NCI-CTCAE Grade 5 corresponds to death (related to AE).

Where:

- **Mild:** symptoms do not alter the subject's normal functioning
- **Moderate:** symptoms produce some degree of impairment to function, but are not hazardous, uncomfortable or embarrassing to the subject
- **Severe:** symptoms definitely hazardous to wellbeing, significant impairment of function or incapacitation.

- **Life threatening:** any event that places the subject at immediate risk of death from the event as it occurred, i.e. it does not include a reaction that, had it occurred in a more severe form, might have caused death (also see Section 8.1.3).

